## 2.3.2.1 Single Patient Dose Escalation Segment (Completed)

In the initial Single Patient Dose Escalation Segment, four 1-patient mini-cohorts (constituting, in aggregate, Cohort 0) were used to examine the effects of one 4-week cycle of
very low doses of flotetuzumab, at doses of 3, 10, 30 and 100 ng/kg/day, administered on a 4 days on/3 days off schedule. This initial phase of the study was implemented to cautiously establish an acceptable starting dose for the second segment of the study, in view of the potential for systemic cytokine production with this T-cell activating molecule.

Each mini-cohort consisted of one patient unless that patient experienced  $a \ge Grade 2 AE$  not clearly related to the underlying disease or  $\ge Grade 3$  infusion-related reaction (IRR, including cytokine release syndrome [CRS]) in the first 28 days of treatment. The appearance and severity of IRRs has been greatly reduced with the introduction of steroid medication prior to flotetuzumab administration (Section 6.4.1.1); Grade 2 IRRs should be considered an acceptable toxicity in the context of flotetuzumab administration in this patient population. Any other  $AE \ge Grade 2$ , or  $\ge Grade 3$  IRR or CRS necessitated expansion of the dose level with enrollment of an additional 3 patients at the same dose level. Use of the next dosing level occurred only if < 2 patients in the resulting 4-patient cohort experienced a DLT and all patients on that dosing sequence had completed the first 21 days of treatment (i.e., received at least 75% of planned dosing). Transition to the Multi-patient Dose Escalation Segment of the study was based on review of the aggregate safety data on all patients participating in Cohort 0.

# 2.3.2.2 Multi-Patient Dose Escalation Segment and Determination of MTDS (Completed)

The Multi-patient Dose Escalation Segment employed a classical 3 + 3 dose escalation study design including cohorts of patients with either AML or MDS. Prior to Amendment 5, all patients in this segment were to be treated with 100 ng/kg/day for 4 days on/3 days off in Week 1, followed by a step-up dose (to 300, 500, 700, 900, or 1000 ng/kg/day in Cohorts 1, 2, 3, 4, and 5, respectively) for 4 days on/3 days off in Week 2 and beyond. This step-up dosing followed the GLP toxicology study in which intra-monkey dose escalation appeared to enhance tolerability of flotetuzumab, apparently through reduction in cytokine release. Starting with Amendment 5, two modifications to the dosing scheme were made. The first was to include an additional step-up dose (two-step lead-in dose: 30 ng/kg/day for 3 days followed by 100 ng/kg/day for 4 days) during the first week of dosing to minimize the extent of IRR/CRS (cytokine release syndrome). The second was to evaluate, in parallel, a 7-day continuous infusion schedule in Weeks 2-4 during Cycle 1, to ameliorate IRR/CRS and AML circulating blast rebound noted with intermittent (4 days on/3 days off) dosing. The patients on the continuous infusion schedule were to receive the two-step lead-dose in Week 1, followed by 300, 500, 700, 900, and 1000 ng/kg/day in Cohorts 6, 7, 8, 9, and 10, respectively, in Week 2 and beyond.

The introduction of the two-step lead-in dose during Week 1 of Cycle 1 was justified by both the pre-clinical toxicology studies and the data observed during the evaluation of Cohort 0 and Cohorts 1 and 2 in the Multi-patient Dose Escalation segment. Nine of 10 of these patients treated with 100 ng/kg/day in the first week had Grade 1-3 IRR/CRS. Patients who went on to receive higher doses (300 ng/kg/day in Cohort 1 and 500 ng/kg/day in Cohort 2) still experienced IRR/CRS upon reintroduction of flotetuzumab in Week 2, but the severity was consistently the same or less than in week one despite the increase in dose. To fully

evaluate the effect of the two-step lead-in dose on the incidence and severity of IRR/CRS in Weeks 1 and 2, the Cohort 2 dose level (500 ng/kg/day in Weeks 2 and beyond) was re-evaluated using the two-step lead-in approach.

Evaluation of treatment by 7-day continuous infusion commenced at the 300 ng/kg/day dose level as this dose level was determined to be safe during dose escalation under Amendment 4 and was predicted to have approximately the same exposure and total dose administered as in Cohort 2 (500 ng/kg/day 4 days on/3 days off starting in Week 2), which had demonstrated acceptable tolerability. This was done in parallel with determination of the maximum tolerated dose (MTD) in the 4 days on/3 days off schedule. Dose escalation in the two schedules proceeded independently, although data from all treated patients was used for dose escalation decision making. With continuous 7-day infusion, the total dose administered was higher at any given dose level (**Table 1**). This correlates with the observed toxicity to date, IRR/CRS, which had been related to  $C_{max}$  (initially occurring within the first 24 hours) and not to total exposure.

	Dose Levels: Weeks 1/Weeks 2-4				
Schedule	Cohort 1 or 6 30  -100/300	Cohort 2 or 7 30  -100/500	Cohort 3 or 8 30-100/700	Cohort 4 or 9 30-100/900	Cohort 5 or 10 30-100/1000
Cohorts 1-10 (total dose Week 1)	Cohort 1: 400 ng  Cohort 6: 490 ng	Cohort 2: 400 and 490 ng  Cohort 7: 490 ng	490 ng	490 ng	490 ng
Cohorts 1-5 (total dose Weeks 2-4): 4 days on/3 days off	3600 ng	6000 ng	8400 ng	10800 ng	12000 ng
Cohorts 6-10 (total dose Weeks 2-4): 7-Day infusion	6300 ng	10500 ng	14700 ng	18900 ng	21000 ng

Table 1	Planned Total Dose Administered in Cycle 1
---------	--

At the 300 ng/kg/day level (Cohort 1), no 30 ng/kg/day lead-in dose was studied for the 4 days on/3 days off schedule; at the 500 ng/kg/day level for the 4 days on/3 days off schedule (Cohort 2), Week 1 was studied  $\pm$  the 30 ng/kg/day lead-in dose.

As of 28 July 2017, by agreement of the Sponsor's Medical Monitor, the Sponsor's Pharmacovigilance Physician, the independent Data Safety Monitor (DSM), and participating Investigators, the MTD in this study has been established as 500 ng/kg/day across both dosing schedules. The 7-day on schedule was selected to open the Cohort Expansion phase of the study, because it was tolerated and potentially offers better anti-leukemic activity. The recommended MTDS was therefore defined as initial two-step lead-in dose on Week 1 followed by 500 ng/kg/day administered by continuous intravenous infusion.

# 2.3.2.3 Cohort Expansion Segment (Ongoing)

#### **Dosing Modifications**

Implementation of the two-step lead-in dose with Amendment 5 decreased IRR/CRS severity compared to the single-step lead-in dose (20). However, data from a cynomolgus monkey toxicology study revealed that large step-up dose intervals were less well-tolerated than smaller increments (data presented in the flotetuzumab **Investigator's Brochure**). Hence, as of Amendment 8, the lead-in dose was modified from a two-step lead-in dose to a multi-step lead-in dose, comprised of sequential smaller and more frequent dose increments (30 to 60 to 100 to 200 to 300 to 400 to 500 every 24 hours) until reaching the MTD of 500 ng/kg/day. Although more involved, it was anticipated that this more conservative approach to intrapatient dose escalation may further attenuate IRR/CRS.

Prior to Amendment 9, all patients eligible to receive flotetuzumab beyond Cycle 1 received drug on a 4 days on/3 days off schedule in Cycle 2 and beyond. With Amendment 9, dosing was modified to specify 2 treatment phases, "Induction" (up to six 28-day cycles of continuous IV infusion [with multi-step lead-in dosing during Week 1 of Cycle 1] until response criteria were met), followed by "Consolidation" (up to two 28-day cycles of 4 days on/3 days off each week). With Amendment 11 all cycles of flotetuzumab, whether induction or consolidation, will be administered as a continuous infusion in 28 day cycles (see Figure 5 and Section 4.1).

In summary, flotetuzumab is dosed as a continuous infusion based on data from the current trial, and centered around two basic premises. Firstly, in some patients that have not achieved full remission and are treated on intermittent dosing, rebound of peripheral blood AML blasts during the period off flotetuzumab has been observed; secondly, elimination of on-off interruptions in treatment with flotetuzumab may help further limit IRR/CRS.

#### **Selection of Target Patient Population**

Both relapsed or refractory AML and Intermediate-2/High Risk MDS patients in whom methylating agents have failed were evaluated in the initial phases of the study. CD123 is expressed on stem cells in both diseases, and both are treated similarly in clinical practice. As such, there is rationale for also evaluating treatment of MDS with flotetuzumab. Allowing both MDS and AML during dose escalation hastened identification of a safe dose to be evaluated in expansion. Given the similarity between MDS and AML in both clinical presentation and pathologic progression, it was expected that the two would behave similarly in response to flotetuzumab. As of Amendment 7, the Sponsor stopped enrolling patients with MDS into this study.

Published translational data (44) suggested that AML patients resistant to chemotherapy displayed an immune infiltrated bone marrow tumor microenvironment, leading to the hypothesis that immunotherapy could be effective in this population. The protocol therefore aimed to enrich the expansion cohort for patients with primary refractory disease (defined as, prior to Amendment 9, leukemia refractory to  $\geq 2$  induction attempts (primary induction failure; PIF), leukemia in first relapse with initial CR (CR1) duration < 6 months (early

relapse; ER), or prior treatment failure with at least four cycles of a hypomethylating agent). The initial 24 patients enrolled under Amendment 7 were restricted to 75% (i.e., 18/24) with primary refractory AML. Guided by response data from the first 24 patients, the Sponsor further restricted enrollment to PIF and ER (CR1 < 6 months) patients. Under Amendment 9, enrollment was restricted to patients with PIF AML (defined as leukemia refractory to  $\geq 2$  [or  $\geq$  1 for patients > 65 years of age] induction attempts, or leukemia in first relapse with initial CR1 duration < 6 months). Under Amendment 10, PIF AML was further defined as leukemia refractory to induction attempts, including but not limited to (1) leukemia refractory to  $\geq 1$ intensive induction attempt(s), per institution, or (2) for adults who are age 75 years or older, or who have comorbidities that preclude use of intensive induction chemotherapy, leukemia refractory to  $\geq 2$  lower intensity induction attempts; a maximum of up to 2 prior salvage attempts was allowed. With Amendment 11, primary refractory AML was redefined as patients with PIF or ER (see Inclusion Criterion 2). Patients treated solely with hypomethylating agents (HMA) have been excluded from the trial. Greater than 4 cycles of HMA are required to define HMA failure. Previously published data show that HMA treatment leads to upregulation of checkpoint molecules, including PD-L1 (49), and our clinical data suggest that PD-L1 expression decreases flotetuzumab activity (37).

#### **Primary Efficacy Analysis**

Based on study design and conduct, the MTD was defined at 500 ng/kg/day after noting DLT at 700 ng/kg/day. The MTD was also defined as the effective dose, as no complete responses (CR, CRh, CRi [CRn, CRp], or MLFS) were noted at doses below 500 ng/kg/day. The lead-in dose or 'priming' dose is designed to safely reach the MTD. While it is best achieved with a multi-step lead-in dose, patients treated with the two-step lead-in dose had still been able to achieve the dose of 500 ng/kg/day safely. Hence, patients treated at 500 ng/kg/day as a continuous infusion, preceded by either a two-step or multi-step lead-dose, may be included in the primary efficacy population as described below.

The sample size for the primary efficacy analysis is 170 patients, and will include all patients, irrespective of when they were enrolled in the study, that 1) were treated with flotetuzumab at the MTD of 500 ng/kg/day as a continuous IV infusion during Cycle 1, irrespective of two-step or multi-step lead-in dose; and 2) meet the definition of PIF/ER AML based on inclusion criteria as revised in Amendment 11 (see Inclusion Criterion 2).

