#### **Analysis Populations:**

Three populations will be used for analysis, as defined below:

- Efficacy population All patients that have been enrolled under Protocol Amendment 11 or later and treated with flotetuzumab at the MTD of 500 ng/kg/day as a continuous 7-day per week IV infusion during Cycle 1, have received any portion of one dose of flotetuzumab, and met the definition of PIF/ER AML based on inclusion criteria as revised in Amendment 11 (see Section 5.1). This population will be used for the primary analysis of efficacy endpoints.
- Safety population All patients who received any portion of any dose of flotetuzumab. AML and MDS will be analyzed as pooled and separate populations for safety and PK. The analysis of all safety endpoints will be based on the safety population.
- **Response evaluable population** All patients in the efficacy population that have a baseline bone marrow assessment, have at least one post-infusion assessment of their disease status or were removed from the study for reason of documented evidence of disease progression, death or treatment-related adverse event. This population will be used in the summary of response rate as a secondary analysis.

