The primary objective of the study going forward is to assess anti-neoplastic activity of flotetuzumab in AML, as determined by the proportion of patients who achieve CR/CRh (see Section 3 for a full list of current objectives).

A summary of prior study development is provided in Sections 2.3.2.1 to 2.3.2.3 below.

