## 9.1 Determination of Sample Size for Primary Efficacy Analysis

The planned sample size for the pivotal portion of the study under Protocol Amendment 11 onwards is 170 patients, based on a three-stage design.

To determine the sample size under Amendment 11 inclusion criteria, historical reference response rates to standard treatments were ascertained through a meta-analysis based on 5 published studies that included PIF/ER AML patients selected from 963 publications identified through database search (11,12,13,30,36). Based on this analysis, the estimated combined CR/CRh rate was 11.8%, with a 95% confidence interval of 9.4% to 14.7%. The upper 95% CI of 14.7% was chosen as the rate for the null hypothesis (H0) and a target of 23% CR/CRh was established as a clinically meaningful endpoint in this patient population.

A three-stage design with two interim analyses will be employed to test the null hypothesis (H0) of CR/CRh rate = 14.7% against the alternative hypothesis (H1) of CR/CRh rate = 23%. Demonstration of CR/CRh rate improvement (H1) by rejecting H0 at a 1-sided type I error of 0.025 with adequate power (80%) in a sequential design requires 170 patients. Specifically, the planned number of patients and the futility and efficacy boundaries at each stage are as follows:

- a. **First interim analysis:** The first interim analysis will be performed after 40 patients have been enrolled and either have had their responses evaluated or were discontinued for any reason from study treatment prior to their first response assessments. This interim analysis is for futility only, that is, the study enrollment will continue if at least 5 (12.5%) out of 40 patients have response of CR/CRh.
- b. **Second interim analysis:** If the enrollment continues after the first interim analysis, a second interim analysis will be performed after additional 60 patients have been enrolled (100 patients in total) and either have had their response evaluated or were discontinued for any reason from study treatment prior to their first response assessment. This interim analysis is for both futility and efficacy. Specifically,
  - i. If the number of CR/CRh is less than 15 (15%) out of 100 patients, then the study is considered futile and enrollment will be stopped.
  - ii. If the number of CR/CRh is 15 (15%) or greater out of 100 patients, then enrollment will continue.

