- iii. If the number of CR/CRh is 25 (25%) or greater out of 100 patients, then H0 is rejected and the study is considered positive. The enrollment will still continue.
- c. **Final Analysis:** If enrollment continues after the second interim, then the final analysis will be performed after additional 70 patients have been enrolled (170 patients in total) and either have had their response evaluated or were discontinued for any reason from study treatment prior to their first response assessments. If the number of CR/CRh is at least 35 (20.6%) out of the total of 170 patients, then H0 is rejected and the study is considered positive.

The above design yields a 1-sided alpha of 0.005 for the efficacy boundary at the second interim analysis and an overall 1-sided alpha of 0.024 with approximately 80% power at the final analysis. The probability of early termination under H0 (futility) in the first two stages is 55%.

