# 9.6.1 Primary Efficacy Analysis

The primary efficacy endpoint for the AML expansion cohort is the CR/CRh rate, calculated as the proportion of patients in the efficacy population that has achieved a best response of CR (mCR, CRc, or CRm) or CRh at any point during treatment by investigator's assessment, according to IWG AML response criteria (Appendix 3). CR/CRh rate will be summarized for the total combined PIF/ER patients as the primary analysis, as well as for PIF and ER patients separately, and for PIF/ER patients in the response-evaluable population as a sensitivity analyses. A two-sided exact 95% confidence interval will be calculated around response rates.

For the second interim analysis of 100 patients, as well as for the final analysis of 170 patients, all treated patients will be followed for at least 6 months or until death from any cause, whichever occurs first, prior to data cutoff for the analysis. If the trial passes the prespecified efficacy boundary (25% observed CR/CRh rate) at the second interim analysis, a two-sided exact 95% confidence interval as described by Jennison and Turnbull (21) will be produced to account for the bias in the conventional exact confidence interval for fixed sample test.

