4.2 Sample Size Determination

The planned sample size for the pivotal portion of the study as of Protocol Amendment 11 is 170 patients, based on a three-stage design.

To determine the sample size under inclusion criteria, historical reference response rates to standard treatments were ascertained through a meta-analysis based on 5 published studies that included PIF/ER AML patients selected from 963 publications identified through database search (1; 2; 3; 6; 7). The response rate identified by the meta-analysis is based on a random intercept logistic regression model, yielding a combined CR/CRh rate for PIF/ ER AML of 11.8%, with a 95% confidence interval of 9.4% to 14.7% (Figure 1).

Figure 1 Forest Plot for Meta-analysis

Study	Events	Total		Proportion 95%-CI
1, CLASSIC I (FaderI JCO 2012) 2, VALOR (Ravandi Lancet Oncol 2015), Refractory 3, VALOR (Ravandi Lancet Oncol 2015), Early Relapse 4, Admiral (Gilteritinib), Chemo 5, Anti CD33 ADC Gemtuzumab, Phase I 6, Anti CD33 ADC Gemtuzumab, Phase II 7, Venetoclax w/ HMA,or LDAC(2) MDACC, Di Nardo	15 16 13 2 4 2	83 149 129 124 14 36 43		0.181 [0.105; 0.280] 0.107 [0.063; 0.169] 0.124 [0.073; 0.194] 0.105 [0.057; 0.173] - 0.143 [0.018; 0.428] 0.111 [0.031; 0.261] 0.047 [0.006; 0.158]
Fixed effect model Random effects model Heterogeneity: $I^2 = 0\%$, $\tau^2 = 0$, $p = 0.49$		578	0.1 0.2 0.3 0.4	0.118 [0.094; 0.147] 0.118 [0.094; 0.147]

The result obtained with the Bayesian method is consistent with the result of the random intercept logistic regression model (Table 1).

Assumption	Point Estimate	95% Credible Intervals (Highest Posterior Density)	95% Credible Intervals (Equal-tail)
Normal prior, normal (0, var=10000)	11.7%	(9.3%, 14.7%)	(9.2%, 14.6%)
Beta prior, beta (1, 1)	11.9%	(9.4%, 14.6%)	(9.4%, 14.7%)

Table 1Meta-analysis Using Bayesian Method

The upper 95% CI of 14.7% was chosen as the rate for the null hypothesis (H0) and a target of 23% CR/CRh was established as a clinically meaningful endpoint in this patient population.

A three-stage design with two interim analyses was employed to test the null hypothesis (H0) of CR/CRh rate = 14.7% against the alternative hypothesis (H1) of CR/CRh rate = 23%. Demonstration of CR/CRh rate improvement (H1) by rejecting H0 at a 1-sided type I error of 0.025 with adequate power (80%) in a sequential design requires 170 patients. Specifically, the planned number of patients and the futility and efficacy boundaries at each stage are as follows:

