5 STUDY POPULATIONS

Three populations will be used for analysis, the efficacy population, safety population and the evaluable population, as defined below:

- Efficacy population All patients that have been enrolled under protocol amendment 11 or later and treated with flotetuzumab at the MTD of 500 ng/kg/day as a continuous 7-day per week IV infusion during Cycle 1, have received any portion of one dose of flotetuzumab, and met the definition of PIF/ER AML based on Amendment 11 inclusion criteria . This population will be used for the primary analysis of efficacy endpoints.
- Safety population All patients who received any portion of any dose of flotetuzumab. AML and MDS will be analyzed as pooled and separate populations for safety and PK. The analysis of all safety endpoints will be based on the safety population.
- **Response evaluable population** All patients in the efficacy population that have a baseline bone marrow assessment, have at least one post-infusion assessment of their disease status or were removed from the study for reason of documented evidence of disease progression, death, or treatment-related adverse event. This population will be used in the summary of response rate as a secondary analysis.

Patients who die before having a post-infusion disease assessment will be considered evaluable for OS and EFS analyses.

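### Protocol 2.3.2.3 opens the 170-patient primary analysis to patients enrolled at any time, while the synopsis, Sections 9.1 and 9.2 and SAP 4.2 and 5 confine it to Amendment 11 onward

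*Protocol*

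**What the plan says.** Protocol Section 2.3.2.3, Primary Efficacy Analysis, gives the primary analysis a sample size of 170 and says that it "will include all patients, irrespective of when they were enrolled in the study". It sets two conditions: continuous infusion at the MTD during Cycle 1, with either type of lead-in accepted, and the PIF/ER definition as revised in Amendment 11. The sentence just before this also says that two-step lead-in patients may enter the primary efficacy population.

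The other sections set an enrolment limit:

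- Synopsis (Analysis Populations) and Protocol 9.2: "All patients that have been enrolled under Protocol Amendment 11 or later".
- SAP 5: "All patients that have been enrolled under protocol amendment 11 or later".
- Protocol 9.1: "The planned sample size for the pivotal portion of the study under Protocol Amendment 11 onwards is 170 patients".
- SAP 4.2: "The planned sample size for the pivotal portion of the study as of Protocol Amendment 11 is 170 patients".

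Protocol 9.6.1 and SAP 11.1 define the primary endpoint, which is "calculated as the proportion of patients in the efficacy population". Protocol 9.1 states the operating characteristics of the design as "an overall 1-sided alpha of 0.024 with approximately 80% power at the final analysis".

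**The concern.** The protocol gives two answers to the question of who is counted in the pivotal analysis. The trial is single-arm and open-label, and some earlier outcomes were already known when this text was written. Section 2.3.2.3 (Selection of Target Patient Population) says that responses in the first 24 Amendment 7 patients guided the narrowing to PIF and ER. Section 4.1 refers to 21 patients in this study who achieved a CR. How many of those 21 were enrolled before Amendment 11, or meet its PIF/ER definition, is not stated.

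The stated alpha treats all 170 outcomes as not yet seen. If earlier patients could be counted toward the boundaries at 40, 100 and 170, or left out, once their results were known, that alpha would no longer be assured.

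**Working it through.** **1. Can the passages be reconciled?** No. Section 2.3.2.3 (Dosing Modifications) says that the two-step lead-in gave way to the multi-step lead-in as of Amendment 8. A rule that admits two-step patients therefore reaches back before Amendment 8, and Section 9.2 and SAP 5 exclude those patients. Reading the 2.3.2.3 rule as silently limited to Amendment 11 would leave its lead-in wording without a purpose.

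**2. The plan's own figures.** Inputs from Protocol 9.1 and SAP 4.2: p0 = 0.147 and p1 = 0.23; continue if at least 5/40; at 100, stop if fewer than 15 and reject H0 if at least 25; at 170, reject H0 if at least 35. The method is an exact binomial recursion over the three looks, with futility binding:

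P(success) = P(X40 ≥ 5, X100 ≥ 25) + P(X40 ≥ 5, 15 ≤ X100 ≤ 24, X170 ≥ 35)

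| Quantity | Stated | Exact |
|---|---|---|
| Alpha at second interim | 0.005 | 0.0047 |
| Overall alpha | 0.024 | 0.0047 + 0.0192 = 0.0239 |
| Power at 23% | about 80% | 0.3533 + 0.4339 = 0.787 |
| Futility stop under H0 | 55% | 54.6% |

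The design figures hold if the 170 are all new patients.

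**3. Earlier patients carried over.** The documents do not give the number of qualifying earlier patients (m) or their responders (k), so every m and k below is an assumption. The recursion starts at n = m with k fixed, and the remaining 170 − m patients respond at 0.147.

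- m = 40, k = 6: P(success) = 0.0132.
- m = 40, k = 8: P(success) = 0.0396.

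These are conditional on k. Averaged over k ~ Binomial(m, 0.147), the result is 0.0239 for m = 18, 24, 30 and 40, the same as with no carry-over. A fixed decision to pool, made without regard to results, leaves the error unchanged.

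**4. Choosing the reading after seeing k.** Suppose earlier patients are counted only when that raises the chance of success:

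alpha = Σk P(k) × max{P(success | m, k), 0.0239}

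| Assumed m | Type I error |
|---|---|
| 18 | 0.0317 |
| 24 | 0.0330 |
| 30 | 0.0341 |
| 40 | 0.0354 |

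All four exceed the one-sided 0.025 limit in SAP 13.4. They apply to a choice made on the earlier outcomes alone, before new data. If success could be claimed under either reading after all data were in, simulation (400,000 trials per m) gives about 3.5% for m = 18 and 3.8% for m = 40.

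**The case against.** The strongest reply is that the operative rule is already settled. The primary endpoint is computed in the efficacy population, and the synopsis, Section 9.2 and SAP 5 define that population in the same way. SAP 4.1 says that Amendment 11 made the trial a pivotal study going forward. The expansion plans about 271 patients on flotetuzumab alone, 271 − 170 = 101 more than the primary analysis needs, which fits 170 new patients on top of earlier ones but does not prove it. Section 2.3.2 itself says "A summary of prior study development is provided in Sections 2.3.2.1 to 2.3.2.3 below", so the rule sits in a background section. An analyst working from the SAP would not arrive at it. The inflation figures rest on assumed counts and on a choice that no text proposes.

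Most of this stands, and it is why the practical risk is modest. It does not remove the conflict. The rule is current text in a segment marked as ongoing, it is worded in the future tense, and it uses the present sample size and the Amendment 11 criteria. We found no statement of which section takes precedence.

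Two limits also stand. Section 9.1 and SAP 4.2 restrict enrolment only through a sample-size sentence, which is weaker than a population definition. The 21 patients in Section 4.1 are mentioned in an argument for treating beyond progression, and show only that some outcomes were known.

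**Conclusion.** The concern holds and should be fixed. Section 2.3.2.3 is the outlier, is probably leftover text, and contradicts the definition of the pivotal denominator. Under the formal sections the overall alpha is 0.0239, as planned. Pooling alone does no harm to it. The exposure comes from having two readings available when earlier outcomes are known: 3.2% to 3.5% type I error if the reading is chosen on those outcomes, assuming 18 to 40 qualifying earlier patients and a true rate of 14.7% in both groups. These sizes are illustrations, because the documents give neither the number of such patients nor their responses. The contradiction itself does not depend on them.

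**What to change.** In Section 2.3.2.3, Primary Efficacy Analysis:

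1. Replace the clause that waives the date of enrolment with a restriction to patients enrolled under Amendment 11 or later.
2. Delete the sentence closing the first paragraph, which lets two-step lead-in patients into the primary efficacy population.
3. Delete the waiver of lead-in type in condition 1.

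A cross-reference to Section 9.2 would also carry over its any-portion-of-a-dose condition and avoid keeping a second full definition.

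The cost is the wording of one protocol subsection. It changes the analysis-set text only. Dosing, the 170 patients, the boundaries, Sections 9.1 and 9.2 and the SAP stay as they are, and no extra patients or tables are needed.
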